8.5.6 Interim Analysis for Sample Size Adjustment

Our initial protocol included a plan to randomize 136 participants; however, this randomization goal did not account for attrition at the 1- and 6-month driving simulations—the source of our primary endpoints. We were unsure what our level of attrition would be, especially since our sample population was teens with ADHD who can have difficulty following through on commitments.

Hence, our plan was to assess attrition when we reached our sample size of 136 to determine how many additional participants we would need to recruit in order to account for attrition. When we reached our sample size of 136, our calculations suggested that we needed to over-recruit to a randomized sample size of 152 to achieve 136 participants with 1- and 6-month simulator outcomes (primary endpoints) (See 16 Summary of Changes to the Protocol and/or SAP).

8.5.7 Practical Measures to Minimize Bias

To minimize bias, all investigators will remain blinded to participant random assignment until all study measures are completed. The only interim analysis that will be performed concerns safety monitoring to ensure that the FOCAL+ intervention does not result in higher rates of crashes (see section 8.5.1). The person that will view these interim analyses is not a study investigator.

8.5.8 Documentation of Interim Analyses

Monthly, the designated safety reviewer will receive two tables for interim safety monitoring analyses: one summarizing the number of MVC for each randomized group for that month and a second table summarizing the number of cumulative MVCs for each randomized group. Within each table we will specify the number of events with a shock value (i.e., indicative of a MVC). See the templates below:

Current Month: November 2021

Number of Motor Vehicle Accidents for Each Randomized Group

	FOCAL+ (intervention)	Sham Control
Number of motor vehicle accidents		

Cumulative

Number of Motor Vehicle Accidents for Each Randomized Group

	FOCAL+ (intervention)	Sham Control
Number of motor vehicle accidents		

8.6 Multiple Testing

See Section 8.4.5 for statistical adjustments for multiple testing.

9 Summary of Study Data

All continuous variables will be summarized using the following descriptive statistics: mean, standard deviation, median, maximum and minimum. The frequency and percentages of observed levels will be reported for all categorical measures. In general, all data will be listed, sorted by intervention group and subject, and when appropriate by visit number within subject. All summary tables will be structured with a column for each treatment in the order (Full Sample, FOCAL+, Sham Control) and will be annotated with the total population size relevant to that table/treatment, including any missing observations.

9.5 Subject Disposition

Operational definitions used to establish how many subjects reached the various stages of the trial are listed below:

- 1) Number Screened: Screening for the study will be defined as any contact between an interested individual who queries about the study and is screened for potential eligibility as

described in 6.1 Recruitment. We will track the number of individuals who are screened for the study.

[figure not shown]
- 2) Consent: Consent will occur during the first study visit (also known as Baseline/Diagnostic and Clinical Assessment).
- 3) Number Eligible: Of those who consented to the study, the number who met all eligibility criteria and who showed up for the initial training visit (when randomization occurred).
- 4) Randomized: Randomization will occur at the second study visit. A sealed envelope will contain the participant's randomization
- 5) Completed intervention/training visits 1-5: Participants will be considered to have completed the intervention/training visit if they complete at least 1 training.
- 6) Completed study 1-month post-training follow-up: Participants will be considered to have completed the 1-month post-training follow-up visit if they complete at least one of the two assessment drives.
- 7) Completed study 6-month post-training follow-up: Participants will be considered to have completed the 6-month post-training follow-up visit if they complete at least one of the two assessment drives.
- 8) Completed DriveCam follow-up: Participants will be considered to have completed the DriveCam follow-up if we are able to obtain DriveCam data within the previously specified analysis time window (See 6.4 Study Assessments section).

We will track many subjects reached the various stages of the trial, how many dropped out and for what reasons (death, treatment failure, withdrew consent).

Resolving multiple or ambiguous visit dates

Research assistants will be trained to keep detailed logs of each study visit noting any deviations in the study visit protocol (e.g., visit rescheduled because teen took their stimulant medication). If there is any ambiguity arising from multiple sources of visit date, we will examine research visit logs to understand the reason for multiple visits. Using this information, we will decide which visit data to use in final analyses.

Skeleton CONSORT flow diagram

9.6 Derived variables

- **Participant Age:** (moderator for supplemental analyses). Age will be measured in years (using decimals; range 16.00-19.99) and will be calculated by subtracting the participant’s date of baseline visit from their date of birth
- **Stimulant medication status:** dichotomized based on whether the teen reported taking ADHD medication at any point during the 12-months of naturalistic driving.

9.7 Protocol Deviations

All protocol deviations will be documented in accordance with IRB requirements in a ‘Protocol Deviation Log’. We will evaluate the deviation log at the end of the study and determine if any of the deviations require statistical consideration or adjustment.

9.8 Demographic and Baseline Variables

The data set will be summarized by treatment groups with respect to important confounders. The distributions of categorical variables will be tabulated by treatment group and overall. Continuous variables will be summarized as mean, median, and standard deviation by treatment group and for the overall sample.

- Age in years
- Age at licensure
- State of licensure
- Gender
- Race
- Ethnicity (Latino/a; Not Latino/a; Unknown)

Trial of Training to Reduce Driver Inattention in Teens with ADHD

- Maternal/Paternal education (highest level)
- Family income
- License Type (Graduated driver’s license; full unrestricted license)
- Driving experience (calculated as months since licensed)
- Full Scale IQ
- Number on stimulant medication at baseline
- Number on stimulant medication during 1-year of post-training driving
- VAPRS scores (Inattention, Hyperactivity/Impulsivity, and Total Score)
- K-SADS ODD diagnosis
- K-SADS Anxiety Disorder diagnosis
- K-SADS Mood Disorder diagnosis

9.9 Concurrent Illnesses and Medical Conditions

Relevant concurrent illnesses, medical conditions, and mental health diagnoses will be assessed as part of the screening and/or the Baseline/Diagnostic and Clinical Assessment. Relevant concurrent illnesses, medical conditions and mental health diagnoses are below along with the methods for assessing them:

Exclusionary concurrent illnesses, medical conditions, and mental health diagnoses:

Concurrent Illness/Medical Condition/Mental Health Diagnosis	Time Point Assessed	Method of Assessment
High-Risk Substance Use	Baseline	Simple Screening Instrument for Alcohol and Other Drugs (SSI-AOD) score ≥ 4
History of moderate to severe head trauma	Screening	Self-report of having lost consciousness for over 30 minutes or having multiple instances of traumatic brain injury irrespective of severity

Non-exclusionary concurrent illnesses, medical conditions, and mental health diagnoses:

Concurrent Illness/Medical Condition/Mental Health Diagnosis	Time Point Assessed	Method of Assessment
Comorbid mental health diagnosis (e.g., oppositional defiant disorder)	Baseline	Kiddie Schedule for Affective Disorders and Schizophrenia for School-Age Children-Present and Lifetime Version (K-SADS-PL)—semi-structured interview with parent and teen
History of head trauma not meeting criteria for moderate to severe head trauma	Screening	Self-report of head trauma that did not meet criteria for moderate to severe. Participants will be required to wait 30 days after their head trauma before participating in the study, to allow sufficient time to pass that negative sequela do not develop.

9.10 Treatment Compliance

The number of treatment sessions attended will be used to assess treatment compliance.

10 Efficacy Analyses

10.5 Primary Efficacy Analysis

Generalized estimating equations (GEE) will be used to analyze the two primary endpoint driving simulator outcome measures: standard deviation of lane position and number of long off-road glances. Missing data will be handled as discussed above (8.4 Missing Data). GEE with an independent correlation structure and accounting for clustering within participants will be conducted for each outcome. Group (FOCAL+ vs. Sham Control), driving timepoint (baseline, 1-month post-training, 6-months post-training), and the two relevant interaction terms: 1) Group x Timepoint (baseline vs. 1-month) and 2) Group x Timepoint (baseline vs 6-month) terms will be tested. Standard deviation of lane position will be analyzed as a continuous variable assuming a normal distribution with a identity link function and an independent correlation matrix. Prior sensitivity analyses showed number of long off-road glances could be analyzed assuming a Poisson distribution with a natural logarithmic link function. Adjusted mean differences for between-group comparisons of standard deviation of lane position (a continuous variable) will be reported by specifying a 'multiple group' option allowing for the two outcome measures to be predicted by months of driving experience separately for the two treatment groups in the same analysis. The resulting intercepts for the outcomes are, by definition, covariate adjusted means. Exponentiated incidence rate ratio for count of long glances during driving simulation will be computed and reported. Note that we will report the exponentiated incidence rate ratio rather than adjusted mean difference for count of long glances because this is the statistic we have seen used for comparing two group counts (Zou, 2004). Confidence intervals for both adjusted mean difference and exponentiated incidence rate ratios will be computed.

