8.3 Covariates and Subgroups

For all analyses:

- Driving experience: Defined as baseline date minus the date that the teen received their graduated or full unrestricted license. Computed in months.

Specific to driving simulation analyses:

- Driving runs: Included in order to be able to include primary outcomes from the two driving runs conducted at the baseline, 1-month post-training assessment, and the 6-month post-training assessment. Generalized estimating equation (GEE) analyses allowed driving simulation data from the two "runs" nested within each of the three "drive types" nested within each participant to be modeled as correlated response variable data, but main or interaction effects for "runs" were not of theoretical interest.

Specific to DriveCam analyses:

- To account for variability in the length of time the DriveCam camera was installed in each participants' automobile during the 1-year post-training period was included as a covariate in addition to months of driving experience as detailed above.

Supplemental Analyses (Requested by New England Journal of Medicine reviewers, editor, and/or statistical expert)

- Moderation Effects—These analyses are post-hoc; thus, effects (adjusted mean difference or relative risk and 95% CI) will be reported rather than significance testing. Note that the widths of confidence intervals are not adjusted for multiple comparisons and no definite conclusions can be drawn from these results.

- Medication status dichotomized based on whether the teen reported taking ADHD medication at any point during the 12-months of naturalistic driving.
- COVID-19 Sensitivity Analysis
 - For 56 (FOCAL+: n=29 teens; Control: n=27 teens) of the 152 participants, their 1-year of naturalistic driving included days beyond March 15, 2020 when COVID restrictions were put into place. We will conduct a sensitivity analyses of our naturalistic driving results by re-running our primary and secondary analyses but including only the 96 teens (FOCAL+ n=47; Control n=49) whose 1-year of naturalistic driving ended prior to COVID restrictions.

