8.5.5 Adjustment of Confidence Intervals and p-values

Because we have two primary endpoints (number of extended glances away from the roadway and SDLP during driving simulation) that are collected at 2 primary endpoints (1-month post-training and 6-months post-training), we have 4 statistical tests for our primary hypotheses. In order to control for potential Type 1 error, we will use a Bonferroni-corrected alpha of .0125 for testing statistical significance.

Confidence intervals for relative risk ratios effect sizes for the secondary DriveCam data analyses will be obtained based on GEE analysis results. Note that the widths of confidence intervals are not adjusted for multiple comparisons and no definite conclusions can be drawn from these results.

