Further, statistical models for examining intervention effects on DriveCam outcomes were modified to allow us to use multilevel mixed longitudinal linear models. Specifically, each participant will have repeated measures response variable data collected over time (i.e., level 1), and within each participant, these responses are not independent but correlated. However, the interest is between-participant variation (level 2) as explained by random assignment. This means within-participant (level-1) variation is not of interest to answering the treatment effect research question, but such variation must be either modeled or controlled appropriately to avoid Type-1 inferential errors. To do so, participant will be declared as the level 2 clustering variable, and specific commands in Mplus (‘Type = Complex’) will be used to: 1) estimate the intra-class correlation (ICC), which quantifies the non-independence of response variable data, 2) compute the design effect ($= C - 1 * ICC$), which is the multiplier needed to be applied to standard error estimates to avoid Type-1 errors, and 3) test the effect of randomization on binary indicators of crash/near-crashes (1=yes, 0=no) and presence of 2-second off-road glances (1=yes, 0=no). Further, it is well-known that analytic techniques such as ‘Type=Complex;’ will only accurately correct parameter estimate standard errors if the number of clusters at level 2 is greater than 20. By declaring participant as the level 2 clustering unit, and N (or, in this case, C), which is more than sufficient to accurately correct standard errors to obtain an accurate treatment effect estimate.

06/23/2022

The following statistical changes were made based on New England Journal of Medicine reviewer, statistical expert, and editor feedback.

- 1) **Changes to primary analyses.**
 - a. **Reporting adjusted mean differences for Standard Deviation of Lane Position.** Reviewers noted that we should report adjusted mean differences rather than raw mean differences for standard deviation of lane position at 1-month and 6-months post-training.

b. Reporting exponentiated incidence rate ratio for comparing group differences in eye glance data. We now report exponentiated incidence risk ratio for count of long glances during driving simulation. We computed an exponentiated incidence rate ratio which is the appropriate statistic for comparing two counts.

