b. Moderator analyses. We ran a moderator analysis examining age and medication status as moderators of FOCAL+ training effects. For the driving simulation outcomes, we examined whether the improvements from baseline to 1-month post-training and baseline to 6-months post-training were moderated by baseline age or medication status. We ran GEE models like those conducted for the primary analyses as described in 10.1 Primary Analysis, however we inserted the moderator variable in the model, analyzed a fully factorially crossed 4-way interaction model, but assessed the significance of the relevant 3-way interactions (Group x Drive Timepoint: baseline vs. 1-month; baseline vs. 6-months x [Moderator Variable]). For DriveCam outcomes, we examined whether group differences on long glances and crash/near-crashes were moderated by baseline age or medication status. We ran multi-level generalized linear mixed models with a logit link function similar to those conducted for the secondary analyses as reported in the manuscript, however we inserted the moderator variable in the model and assessed the significance of the 2-way interaction between Group x [Moderator Variable].

08/15/2022

The following statistical changes were made based on New England Journal of Medicine statistical expert and editor feedback.

1) Supplemental analyses were trimmed to analyses for which we could provide a strong rationale. Specifically, we will only report moderation analysis of the medication on training outcomes and COVID-19 sensitivity analyses.

a. Medication Moderation. For the driving simulation outcomes, we examined whether the improvements from baseline to 1-month post-training and baseline to 6-months post-training were moderated by medication status. These analyses were not intent-to-treat since only the 140 teens for whom we had information about medication status during the 1 year of follow-up were included in these analyses. Adjusted mean differences for standard-deviation of lane-position and natural logarithmic incident rate ratios for count of long glances were computed

using multiple group analysis methods. Specifically, conditional on months of driving experience, training group difference statistics were computed separately across binary medication status.

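### The primary analysis in SAP 10.5 never conditions on the baseline simulator outcome that every teen has, and the contrast behind the glance rate ratio is not stated: a loss of precision and a labelling gap, with no bias from the handling of baseline

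*Combined protocol and SAP*

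**What the plan says.** SAP 10.5 analyses each simulator outcome by GEE with an independence working correlation, clustered on participant. The model contains "Group (FOCAL+ vs. Sham Control), driving timepoint (baseline, 1-month post-training, 6-months post-training), and the two relevant interaction terms", namely group by baseline vs 1-month and group by baseline vs 6-month. SAP 8.5.5 counts the same structure: with two endpoints and two visits, "we have 4 statistical tests for our primary hypotheses", each at a Bonferroni alpha of .0125.

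The reported SDLP estimate comes from a multiple-group fit that allows the outcomes "to be predicted by months of driving experience separately for the two treatment groups in the same analysis"; the intercepts are taken as adjusted means. Glances are reported as an exponentiated incidence rate ratio. Then "Confidence intervals for both adjusted mean difference and exponentiated incidence rate ratios will be computed", with no confidence level given and no visit named in that section.

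Elsewhere, SAP 5.2 defines both endpoints at 1 and 6 months. The June 2022 entry in SAP 14.7 records the advice that "we should report adjusted mean differences rather than raw mean differences for standard deviation of lane position at 1-month and 6-months post-training". The August 2022 entry, on moderation, says "we examined whether the improvements from baseline to 1-month post-training and baseline to 6-months post-training were moderated by medication status". SAP 8.2.1 states that all participants have a baseline simulation. SAP 8.3 lists driving experience as the covariate for all analyses and describes driving runs as "Included in order to be able to include primary outcomes from the two driving runs conducted at the baseline, 1-month post-training assessment" and at 6 months. No section lists baseline SDLP or baseline glances as a covariate.

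**The concern.** There are two linked problems.

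1. **Precision.** Baseline is measured before randomization on everyone. Using it as a response level subtracts it with a fixed coefficient of 1; using it as a covariate lets the data choose the coefficient. The tested term does the first. The reported SDLP difference, if it is a follow-up contrast, does neither.
2. **Labelling.** If the p-value comes from a change contrast and the interval from a follow-up contrast, the two belong to different estimators of the same effect and can fall on opposite sides of the decision. A reader of the glance result cannot tell whether the rate ratio is the tested ratio of ratios or a plain group ratio at one visit.

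The four tests concerned are the trial's confirmatory ones.

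**Working it through.** **Inputs from the documents.** Four primary tests at .0125 (SAP 8.5.5). 152 randomized to obtain 136 completers (SAP 7), that is 76 or 68 per arm. Planning effects .6 and .10 (Protocol 5.f.2.a.1), so d = .6 − .10 = .5. The protocol set these for glances and assumed a comparable effect for driving performance.

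**Assumed.** Two-sided tests; equal baseline and follow-up SDs; d in follow-up SD units; one summary value per visit; baseline to follow-up correlation rho of .8, .5 and .3. The .80 in Protocol 5.e.1 is a test-retest figure cited from an on-road driving test source, not this trial's simulator.

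**The plan's own figures.** .05/4 = .0125 reproduces. Attrition of 16/152 = 10.5% gives 136/.895 = 152. The protocol's 99% power at 68 per group is for a main effect of group in the earlier ANCOVA, not for this interaction. A single comparison at two-sided .05 and d .5 gives 83%, and the 99% depends on an unstated correlation among visits. Nothing below relies on it.

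**Per-person variance at one visit, SD = 1**
- change, as tested: 2(1 − rho)
- follow-up only: 1
- baseline-adjusted: 1 − rho²

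Ratios to the adjusted variance are therefore 2/(1 + rho) for change and 1/(1 − rho²) for follow-up only. Power is from the noncentral t.

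| rho | change / adjusted | follow-up / adjusted | Power, tested vs adjusted, 68 per arm | Same, 76 per arm |
|---|---|---|---|---|
| .8 | 1.11 | 2.78 | 98.0 vs 98.9% | 99.0 vs 99.5% |
| .5 | 1.33 | 1.33 | 64.9 vs 79.7% | 71.0 vs 84.7% |
| .3 | 1.54 | 1.10 | 47.5 vs 69.9% | 53.2 vs 75.8% |

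If d = .5 is instead in change-SD units, power at 68 per arm is 64.9% for the tested term at every rho, against 70.5, 79.7 and 85.9% adjusted.

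**Unequal SDs.** With baseline SD s0 and follow-up SD s1, the change variance minus the adjusted variance is (s0 − rho·s1)². This is never negative, and it is zero when s0 = rho·s1. At rho .8:
- s1 = 1.25·s0: change 1 + 1.5625 − 2 = .5625; adjusted 1.5625 × .36 = .5625; ratio 1.00.
- s1 = .8·s0: change 1 + .64 − 1.28 = .36; adjusted .64 × .36 = .2304; ratio 1.56.

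**Disagreement, only if the reported SDLP difference is a follow-up contrast.** 400,000 simulated trials per setting, 98.75% CI, rho .8 / .5 / .3:

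| | 68 per arm | 76 per arm |
|---|---|---|
| test significant, CI includes 0 | 34 / 15 / 8% | 28 / 14 / 7% |
| test not significant, CI excludes 0 | 1 / 15 / 25% | 0.4 / 14 / 25% |
| total | 34 / 31 / 33% | 29 / 28 / 32% |

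**Bias.** In GEE simulations with a true SDLP effect of −.5, all three contrasts averaged −.49 to −.51. For glances (assumed Poisson-lognormal counts, true rate ratio .6), all three recovered .598 to .602. The planned contrast there had 1.16 to 1.52 times the variance of a model with log(baseline + 1).

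**Centring.** The SDLP intercepts have arm-specific slopes on driving experience. SAP 10.5 does not say that the covariate is centred. If it is not, the difference of intercepts refers to a teen with 0 months of experience. Illustration: mean experience 12 months, slopes differing by .02 SD per month, average effect −.50; the intercept difference is −.50 − 12 × .02 = −.74.

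**The case against.** The planned test is prespecified, valid and consistent with the four tests in SAP 8.5.5, so preferring baseline adjustment is a choice of efficiency and not the correction of an error. That stands, and it is why the planned test should not be replaced once results are known. It does not remove the gain, which needs no new data.

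The size of the gain is not fixed by the documents. At the only correlation they mention, .80, the tested term loses about 1 power point. The losses of 15 and 22 points at rho .5 and .3 rest on assumed values. A reader might infer that the trial is underpowered by that much, or that the tested term is less precise at every rho below 1. Neither follows: the trial's rho and SD ratio are not given, and with unequal SDs the loss can vanish.

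On labelling, the SDLP half is weaker than the glance half. SAP 5.2 and 14.7 most naturally place the SDLP difference at 1 and 6 months, and the improvement-from-baseline wording belongs to a post-hoc moderation analysis. A reader might infer that p-value and interval certainly come from different contrasts. The documents do not say so; it is the more natural reading for SDLP and an open question for glances. The disagreement rates also do not mean that the estimates conflict: both contrasts target the same effect, and they differ in which side of a threshold they fall on.

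A reader might also infer bias from chance baseline imbalance. The interaction removes imbalance by subtraction, and a follow-up contrast is unbiased under randomization. The centring point is separate.

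**Conclusion.** The concern holds in a limited form. Every randomized teen has a baseline value of both primary outcomes, and neither the tested term nor the reported SDLP estimate conditions on it. In large samples adjustment cannot lose precision against either contrast. How much it gains depends on a correlation and an SD ratio that the documents do not give.

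If rho is near .8 with equal SDs, the test is almost unaffected and the main cost is in the reported SDLP interval: a follow-up-only difference has 2.78 times the adjusted variance, so an interval about 1.67 times as wide (√2.78). If rho is nearer .3 to .5, the test itself loses materially.

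What the glance rate ratio represents, the confidence level, and the centring of driving experience should be stated in any case. The absence of bias applies to the handling of baseline only; it does not cover intercepts from an uncentred covariate. This is worth changing, with medium confidence in its practical size.

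**What to change.** Fit one GEE per outcome:
- Responses: the 1- and 6-month runs.
- Terms: group, visit, group by visit, and run.
- Covariates: the teen's baseline value (mean of the two baseline runs for SDLP; log-transformed baseline count for glances, with the transform fixed in advance) and driving experience centred at its mean.
- Participant-clustered robust standard errors.
- Estimate, p-value and 98.75% CI at each visit, all taken from this model.

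Make it primary only if results are not known. SAP 14.7 suggests that they are: its 2022 entries answer journal review and describe models "similar to those conducted for the secondary analyses as reported in the manuscript". In that case:
- keep the planned interaction test as primary;
- report that term's own estimate and 98.75% CI beside its p-value (difference in change for SDLP, ratio of rate ratios for glances);
- label any other contrast by type and visit;
- state the centring;
- add the model above as a dated sensitivity analysis.

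Keep baseline in the SAP 8.4 imputation models and check that they are compatible with the new model.

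Cost: wording in SAP 10.5, one extra model per outcome, and the compatibility check, possibly with a re-run of the 100 imputations. There are no new data, and the four hypotheses and the alpha are unchanged.

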6.2 Inclusion-Exclusion Criteria and General Study Population

Inclusion Criteria

Participants for the study must meet all the following criteria:

- a. Consent: The family must provide signature of informed consent by parents or legal guardians. Eighteen-year-old adolescents must provide their own consent.
- b. Assent: Adolescents under the age of 18 must provide a signature indicating assent to participate in the study
- c. Aged 16-19.
- d. Teens in ADHD group will meet DSM ADHD criteria for ADHD-Predominantly Inattentive Presentation or ADHD-Combined Presentation based on the K-SADS interview. For research purposes, we will utilize criteria specified in the DSM-5 for older adolescents (i.e., a teen will qualify for an ADHD diagnosis with 5 or more inattentive and/or 5 or more hyperactive impulsive symptoms with related impairment across multiple settings) for all teens.
- e. Possess a valid driver's license and regularly spend at least 3 hours per week engaged in unsupervised driving. **Rationale:** Must be legal for participant to drive independently since driving risk among teen drivers is greatest in absence of adult supervision (Williams, 2003). Further, there is a need to collect ample DriveCam outcome data during unsupervised driving conditions to test for intervention effects. Other driving studies have used similar inclusion criteria for number of hours of independent driving (Nichols, 2012).
- f. Participant has an IQ (Intelligence Quotient) ≥ 80 on at least one standard score or composite score as determined by the Kaufman Brief Intelligence Test—2nd edition. **Rationale:** Teens with cognitive challenges may not be able to understand intervention instructions.
- g. Parent willing to participate. **Rationale:** Teens will be asked to refrain from taking medication on days of driving assessment (i.e., driving simulation). Since driving to our facility for testing without taking medication may put the teen at risk, a parent will need to agree to drive the teen to these visits. Parents will also be participating in the intervention.
- h. Participants are permitted to be on medication except for those participants taking medication prescribed to manage ADHD symptoms that cannot be washed out on days they use the simulator, and neuroleptic medications. For participants taking stimulant medications for their ADHD, they will not take that medication on the days they complete simulator tasks.

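### Section 10.5 treats multiple-group intercepts as covariate-adjusted means without stating the value of driving experience at which they are evaluated; read literally, the SDLP difference and CI are those at 0 months since licensure

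*Combined protocol and SAP*

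**What the plan says.** SAP Section 10.5 sets out the primary model: "GEE with an independent correlation structure and accounting for clustering within participants will be conducted for each outcome". SDLP is analysed as normal with an identity link. The effect size to be reported for SDLP, with its CI, is an adjusted mean difference between arms. It comes from a multiple-group option in which the outcomes are "predicted by months of driving experience separately for the two treatment groups in the same analysis", so each arm has its own slope on experience. The section then says: "The resulting intercepts for the outcomes are, by definition, covariate adjusted means".

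The covariate is specified in Section 8.3: "Defined as baseline date minus the date that the teen received their graduated or full unrestricted license. Computed in months". Section 9.8 repeats that it is months since licensure. Neither section, nor any other place that mentions driving experience, gives a centring value or a reference value, or says that the contrast is evaluated at the covariate mean.

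Two other places bear on the point. Section 6.2 requires a valid licence and that the teen "regularly spend at least 3 hours per week engaged in unsupervised driving". Section 14.7 records journal feedback that the authors should "report adjusted mean differences rather than raw mean differences for standard deviation of lane position".

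**The concern.** A regression intercept is the expected outcome where the covariate equals zero. It is an adjusted mean only if zero has been placed at a sensible value shared by both arms. In Section 8.3 zero means a teen licensed on the day of the baseline visit. Such a teen lies at the edge of the population admitted by Section 6.2, which asks for regular weekly unsupervised driving.

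Because the slopes differ by arm, the choice of zero does not cancel out of the between-arm difference. The statistic at stake is the reported effect and CI for one of the two primary endpoints, at 1 month and at 6 months. Someone double-checking the code under Section 13 cannot tell from the SAP which value of experience the result should refer to.

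**Working it through.** The plan gives no figure to reproduce here, so the check is algebra plus simulation.

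**Inputs from the SAP.** 152 randomised (Section 5.1) at 1:1 (Section 6.3), hence 76 per arm; two drives at each of three timepoints (Sections 8.3 and 8.5.4); arm-specific slopes, identity link and independence working correlation (Section 10.5).

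**Inputs assumed.** The mean and SD of months of driving experience are not in the documents. Four pairs are used to show a range: 6/12, 8/8, 12/9 and 16/8 months.

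**Step 1, what the intercept difference is.** Write the fitted line in arm g at one timepoint as a_g + b_g·x, with x in months. The intercept difference a_F − a_S is the contrast at x = 0. The contrast at a common value m is (a_F − a_S) + (b_F − b_S)·m. The two agree only if m = 0 after centring, or if the slopes are equal.

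**Step 2, precision with slopes fitted per timepoint.** Experience is constant within a teen, so with two runs and working independence the fit is ordinary least squares on teen means. The variance of the contrast at 0 is then about the variance at the pooled mean times (1 + mean²/SD²). The CI widens by the square root of that factor: sqrt(1 + 36/144) = 1.12, sqrt(1 + 64/64) = 1.41, sqrt(1 + 144/81) = 1.67, sqrt(1 + 256/64) = 2.24.

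**Step 3, simulation.** The table compares the formula with simulated ratios of cluster-robust SEs, contrast at 0 over contrast at the pooled mean.

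| Assumed mean/SD (months) | Formula | One follow-up, two runs | Three waves, slope per timepoint | Three waves, one slope per arm |
|---|---|---|---|---|
| 6/12 | 1.12 | 1.13 | 1.13 | 1.10 |
| 8/8 | 1.41 | 1.43 | 1.43 | 1.34 |
| 12/9 | 1.67 | 1.67 | 1.69 | 1.56 |
| 16/8 | 2.24 | 2.24 | 2.25 | 2.05 |

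The one-follow-up column used 76 per arm, gamma-distributed months and 1500 replicates per cell. Its ratios barely moved as the within-teen correlation went from 0.3 to 0.9 (2.231 to 2.241 for 16/8).

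The last column is smaller because a slope shared across waves is estimated from each teen's average over waves. The factor becomes sqrt(1 + k·mean²/SD²), where k is the residual variance of that average divided by the single-wave variance. From the table, 1.34² − 1 = 0.80 for 8/8, and (2.05² − 1)/4 = 0.80 for 16/8, so k was about 0.8. In this form the factor does depend on the within-teen correlation.

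**Step 4, bias.** With equal true slopes and an arbitrary true difference of −0.50, mean estimates ran from −0.494 to −0.516 at 0 months and from −0.493 to −0.509 at the pooled mean, so neither is biased. With unequal slopes the shift is the slope difference times mean months. A separate simulation checked this with an invented slope difference of 0.02 residual SD per month and experience uniform on 0 to 48 months (mean 24). The formula gives −0.50 ± 0.02 × 24, that is −0.98 or −0.02; the simulated means were −0.979 and −0.023. This confirms the formula. It does not estimate the shift in this trial, because the documents give no slopes.

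**Step 5, the tests.** Section 10.5 tests the Group x Timepoint terms. If months enters without interacting with both group and time, moving its zero changes the intercept and possibly the group term, but not Group x Timepoint. If covariate-by-group-by-time terms were added to the tested model, the Group x Timepoint coefficients would themselves refer to 0 months.

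None of these simulations included the 100 imputations of Section 8.4.

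**The case against.** The strongest reply is that Section 10.5 names its target. It says adjusted means, and that is correct if months was centred at the pooled mean. Sections 8.3 and 9.8 define a variable; they do not say how it was coded in this fit, and silence on centring is not evidence that there was none. The size rests wholly on assumed means and SDs. Under raw coding with equal slopes, the only consequence is an interval wider than it need be.

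Much of this stands. A reader might infer that the SDLP differences were in fact computed at 0 months. The documents do not show that; they show only that the written rule, followed literally, leads there. A reader might also infer that the primary tests are compromised. As specified, they are not.

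A third inference would be that the plan allows centring each arm at its own mean. Nothing in the text suggests it. It would return the raw mean difference, since a least-squares line passes through its own arm's means, and Section 14.7 moves away from raw differences.

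What the reply does not remove is the false general statement. With arm-specific slopes, the intended adjusted mean is not determined until a common reference value is given, and an analysis plan should give it.

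**Conclusion.** The point holds as a defect in the written plan. The intercepts in Section 10.5 are covariate-adjusted means only if months of driving experience is centred at one value common to both arms, and the SAP states no such value. The literal text gives the SDLP difference and CI at 0 months since licensure.

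If months was entered raw, the CI is too wide by a factor of roughly 1.1 to 2.2 over the assumed range, towards the lower figures if one slope per arm is shared across waves. Which factor applies cannot be settled without the actual mean and SD of experience and the exact slope specification. A shift in the estimate needs arm slopes that differ, and no size can be given for it. The conclusion on the tests rests on the tested model having no covariate-by-group-by-time terms, which is how Section 10.5 reads.

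It would go too far to extend this to the medication-status results. Section 14.7 says only: "Specifically, conditional on months of driving experience, training group difference statistics were computed separately across binary medication status". It does not say that those differences are intercepts.

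**What to change.** In Section 10.5, replace the definitional claim with its condition: months of driving experience is centred at the pooled mean of both arms before the multiple-group fit, or the SDLP contrast and CI at 1 and 6 months are evaluated at that pooled mean. Give the value used, and say that arm-specific means are not to be used for centring. The arm-specific slopes can stay; state whether they are fitted per timepoint or shared across timepoints. A cross-reference from the medication-status analysis in Section 8.3 is enough, to apply if those differences also come from intercepts.

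The cost is one or two sentences and one line of code. If months was already centred at the pooled mean, only the text changes. If it was entered in any other way, the SDLP adjusted means and CIs must be re-run on the 100 imputed datasets. No new data are needed, and the Group x Timepoint tests as specified do not change.
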